When treating major depression with implanted VNS, the widely held belief is that chronic stimulation is required for therapeutic effect. In trials of implantable VNS in major depression, more patients respond at 12 months than at 3 months. Once depressed patients respond to VNS, the effects have been demonstrated to continue for up to five years with continued stimulation. This finding suggests that VNS gradually changes brain function through neuroplasticity.

electoCore has developed gammaCoreTM, (non-invasive vagus nerve stimulator, nVNS) which is FDA approved for the acute and preventive treatment of cluster and migraine headache. It is approved for adults with cluster headache and \ for adolescents and adults (>12 years of age) with migraine. The portable hand-held nVNS device is external to the body and delivers similar results as the implantable nVNS device, without the need for surgery. The device is about the size of a smartphone and will be held to the neck during the nVNS therapy. Each discrete nVNS stimulation lasts two minutes. We plan to use the recommended dosing schedule used in preventing migraine, since the device has demonstrated safety at that dose/duration and has known effects on the brain. We propose using gammaCoreTM (nVNS) to treat treatment resistant depression (TRD) for up to 6 months.

With this study, we will address the following scientific aims:

- 1) Demonstrate the antidepressant effects of nVNS in human adults with treatment refractory MDD as measured by standard rating scales.
- Confirm gammaCore's™ safety profile in adult patients with TRD.

B. Approach
B1. Study Design

Participants will be medically stable and historically have failed to respond to one or more adequate trials of commercially available antidepressant drugs during the current depressive episode. Five adults with treatment resistant depression will participate in this pilot study. We plan to instruct the participant to self-administer nVNS based on guidance from the manufacturer. The study will use an open-label design. The initial phase will be 3 months and the participant will be seen for monthly follow-up office visits following the screening and baseline visits. If the participant improves after the 3 month trial, as determined by a 25% improvement on the primary outcome measure, the Montgomery-Asberg Depression Rating Scale (MADRS), the participant will continue using the device and be evaluated monthly thereafter.

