Analysis plan: The data will first be screened for outliers and structural problems using analytical and graphical methods. If there are violations of normality assumptions, we will determine if power transformations can address this. Otherwise, we will analyze the data using non- and semi parametric methods.

The primary analysis approach will be a generalized linear mixed model. This approach allows modeling within subject correlations of the data in a repeated measurement design and provides unbiased parameter estimates. Time will be modelled as a within subject variable. The main variable of interest in the model will be the time*Tx interaction term. To account for baseline differences between participants we will include random effect terms for each subject.

B2. Inclusion/Exclusion Criteria

Participants will be recruited from the outpatient clinic at the University of Alabama at Birmingham Department of Psychiatry and Behavioral Neurobiology. All recruiting efforts will be coordinated through the existing infrastructure of the Depression and Suicide Center.

Inclusion Criteria:

- 1) Age 18-75 years old
- 2) Sufficient fluency in English to understand testing procedures and provide written informed consent
- 3) A Hamilton Depression Rating Scale total score ≥ 18
- 4) A DSM 5 diagnosis of MDD based on the MINI.

Exclusion Criteria:

- 1) Evidence of alcohol or other substance use disorder in the past 3 months
- 2) For females: current pregnancy or lactation (women of reproductive potential must have a negative urine pregnancy test at screening).
- 3) Depressed patients who have failed at least one adequate antidepressant trial during the current depressive episode based on the ATRQ.
- 4) Diagnosis of other primary psychiatric disorder (defined in this case as being the main focus of treatment) as determined by the MINI, such as: bipolar disorder, personality disorders, psychotic disorders, post-traumatic stress disorder, obsessive-compulsive disorder, dissociative disorders, eating disorder, or cognitive task due to neurological conditions
- 5) Systolic blood pressure < 150 and/or diastolic blood pressure < 90 at screening
- 6) Post-partum state (being within 2 months of delivery or miscarriage)
- 7) Imminent suicide or homicide risk as determined by the investigator
- 8) Being treated with one of the following medications: benzodiazepines or other CNS depressants.

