- 9) No clinically significant neurological disease based on medical history (e.g., epilepsy) or significant head injury.
- 10) Any of the following disorders are exclusionary: Rheumatoid arthritis; Lupus erythematosus; Autoimmune hepatitis; Autoimmune peripheral neuropathy; Autoimmune pancreatitis; Behcet's disease; Crohn's disease; Autoimmune glomerulonephritis; Grave's disease; Guillain-Barre syndrome; Hashimoto's thyroiditis; Autoimmune polymyositis or polymyalgia; Myasthenia gravis; Narcolepsy; Polyarteritis nodosa; Scleroderma; Sjogren's syndrome; Transverse myelitis; Wegener's granulomatosis; History of seizures (only childhood febrile seizures are allowed)
- 11) The presence of clinically significant laboratory findings in the opinion of the investigator including, but not limited to, clinically significant anemia or transaminase elevation is considered exclusionary.
- 12) If the UDS is positive, the subject would be excluded if, in the opinion of the investigator, the positive UDS meant the subject has an active substance use disorder.
- 13) Patients with prior exposure to VNS therapy whether using an implantable or external device will be excluded.
- 14) An active implantable medical device, such as a pacemaker, hearing aid implant, or any implanted electronic device
- 15) A metallic device, such as a stent, bone plate, or bone screw, implanted at or near the neck
- 16) An open wound, rash, infection, swelling, cut, sore, drug patch, or surgical scar(s) on the neck at the treatment location
- 17) Patients diagnosed with narrowing of the arteries (carotid atherosclerosis)
- 18) Patients who have had surgery to cut the vagus nerve in the neck (cervical vagotomy)
- 19) Patients with clinically significant hypertension, hypotension, bradycardia, or tachycardia

B2. Assessments of clinical symptoms, cognition and functioning

Depressive symptoms will be assessed with the Hamilton Depression Rating Scale 17 item version and the Montgomery Asberg Depression Rating Scale. We will also administer the following self-reported questionnaires to characterize reward sensitivity and other personality features relevant to anhedonia: Social Anhedonia Scale, the Motivation and Energy Inventory and the Physical Anhedonia Scale.

C. References

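### As worded, exclusions 5 and 9 each turn away a person with blood pressure below both limits and no neurological disease or head injury, and they run opposite to exclusions 19 and 10

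*Protocol*

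**What the plan says.** Four items under the exclusion heading in protocol section B2 (Inclusion/Exclusion Criteria) matter here:

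- Item 5: "Systolic blood pressure < 150 and/or diastolic blood pressure < 90 at screening".
- Item 9: "No clinically significant neurological disease based on medical history (e.g., epilepsy) or significant head injury".
- Item 10 opens with "Any of the following disorders are exclusionary". Its list includes several disorders of the nervous system, such as myasthenia gravis and narcolepsy, and any history of seizures other than febrile ones in childhood.
- Item 19: "Patients with clinically significant hypertension, hypotension, bradycardia, or tachycardia". It gives no numeric limit.

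Section B1 (Study Design) describes the intended population: "Participants will be medically stable and historically have failed to respond to one or more adequate trials". It does not define medical stability. The second aim in section A is to confirm the device's "safety profile in adult patients with TRD". The SAP contains only the analysis plan and says nothing on eligibility. Neither document restates or corrects item 5 or item 9.

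**The concern.** In an exclusion list, a person who fits an item is out. Item 5 describes readings below the limits, and item 9 begins with a negation. Taken at their word, both remove people with no raised reading and no neurological history. Items 19 and 10 in the same list remove people at the other end.

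These rules decide who receives a device held to the neck, in a study that sets out to confirm its safety. A screener who follows the text turns away people who appear to fit the population in section B1. A screener who follows a presumed intention is using a rule that the protocol does not contain. In either case, a reader of the safety result cannot tell from the documents which rule defined the participants.

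**Working it through.** There is no stated figure to reproduce. The check is a truth table on the wording, with items 5, 9, 10 and 19 taken as exclusions.

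**Item 5.** Let S mean systolic below 150 and D mean diastolic below 90. *And/or* covers two senses: exclude if (S and D), or exclude if (S or D). An exclusive *or* is not open, because the phrase itself includes *and*.

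| Reading | *and* | *or* |
|---|---|---|
| 149/89 | excluded | excluded |
| 150/89 | not excluded | excluded |
| 149/90 | not excluded | excluded |
| 150/90 | not excluded | not excluded |

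A person below both limits is excluded in 2 of 2 senses. The choice of sense matters only when one reading is below its limit and the other is not.

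**Item 9.** Let N mean clinically significant neurological disease and H mean significant head injury. Three parses of the opening *No* were tried:

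- A: *No* covers both conditions together; exclude if not (N or H).
- B: *No* covers the disease only; exclude if (not N) or H.
- C: *No* is carried to each condition separately; exclude if (not N) or (not H).

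| Person | A | B | C |
|---|---|---|---|
| Neither | excluded | excluded | excluded |
| Head injury only | not excluded | excluded | excluded |
| Disease only | not excluded | not excluded | excluded |
| Both | not excluded | excluded | not excluded |

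A person with neither condition is excluded in 3 of 3 parses. The parses differ only for people who have at least one of the conditions.

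**Both items together.** There are 2 × 3 = 6 combinations. A person at 149/89 with neither condition is excluded in 6 of 6. If item 5 alone were corrected, item 9 would still exclude that person in 3 of 3 parses. If item 9 alone were corrected, item 5 would still do so in 2 of 2.

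**Against items 19 and 10.** To pass item 5, a person needs at least one reading at or above its limit (under *and*), or both (under *or*). Item 19 then removes anyone whose hypertension is judged clinically significant. To pass item 9, a person needs disease or head injury (A), disease without head injury (B), or both (C). Item 10 then removes seizures and its listed disorders, which takes out epilepsy, item 9's own example.

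The four items can all be passed together. That takes a reading at or above a limit that is not judged clinically significant hypertension, plus one of the following:

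- a neurological disease that item 10 does not remove: with or without head injury under A, without it under B, with it under C;
- under A only, a significant head injury alone.

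The pairs therefore oppose each other in direction without being logically incompatible. The set left eligible fits poorly with the population in section B1.

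**The case against.** The strongest reply is that the intention is plain. Both items look like conditions to be met that were placed under the wrong heading, and items 10 and 19 and the reference to medical stability all point that way. This is an open-label pilot in five adults, recruited from one named outpatient clinic, and the analysis plan does not depend on these items. Nothing in the documents shows that anyone was wrongly enrolled or turned away. Items 10 and 19 still block seizures, the listed disorders and clinically significant hypertension, so the screen is not simply reversed. The clash with those items is also not a strict contradiction.

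Much of this stands. The misplacement is a likely explanation, the comparison with items 10 and 19 only supports the main point, and the practical consequence is unknown.

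It does not remove the fault, for three reasons:

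- The presumed rule is not in the protocol, and presuming it does not settle item 5. Read as a condition to be met, 150/89 and 149/90 qualify under *or* and fail under *and*, so two screeners with the same guess could decide differently on one person.
- Items 10 and 19 are only a partial backstop. Item 19 has no numeric limit, and no other exclusion names head injury.
- Faulty text extraction is an unlikely explanation. The comparison sign in the inclusion criterion on the Hamilton score came through intact, and the *No* in item 9 is a word. Even a misread sign in item 5 would leave item 9 as it is.

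**Conclusion.** The point holds. As written, items 5 and 9 each exclude a person below both limits with neither neurological condition, in 6 of 6 combinations of the readings tested. Two things are assumed: the items are exclusions, as their heading says, and the signs are as printed. Only treating the items as conditions to be met avoids the result, and that departs from the text.

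The wording of operative eligibility rules gives a wrong result if followed, so it must be fixed. The documents give no prevalences or screening numbers, so the number of people affected cannot be estimated. Nor do they show which rule the clinic used.

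**What to change.** Amend the eligibility list so that item 5 is reconciled with item 19, and item 9 with item 10. The investigator should confirm the intended blood-pressure rule, including how *and/or* operates and on which side the values 150 and 90 fall, and the scope of *No* in item 9. The sponsor should record which rule was actually applied to anyone already enrolled. No limit or clinical rule is proposed here.

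Item 3 can be reconciled in the same amendment. It excludes people who have failed at least one adequate antidepressant trial in the current episode, which is the population section B1 describes. It is a related fault and is not counted in this point.

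The cost is low: a wording change and a short record. No new procedures are needed, because section B1 already schedules vital signs, physical examination and ECG at screening, and item 9 already relies on medical history. The protocol is dated August 30, 2022 and the SAP April 3, 2024, and neither states enrolment status. If enrolment has closed, the record of the rule applied is the part that still has effect.

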Cover Page – Statistical Analysis Plan

Title: Vagal Nerve Stimulation for Treatment Resistant Major Depression

NCT04990687

April 3, 2024

Title: Vagal Nerve Stimulation for Treatment Resistant Major Depression

NCT04990687

Analysis plan: The data will first be screened for outliers and structural problems using analytical and graphical methods. If there are violations of normality assumptions, we will determine if power transformations can address this. Otherwise, we will analyze the data using non- and semi parametric methods.

The primary analysis approach will be a generalized linear mixed model. This approach allows modeling within subject correlations of the data in a repeated measurement design and provides unbiased parameter estimates. Time will be modelled as a within subject variable. The main variable of interest in the model will be the time*Tx interaction term. To account for baseline differences between participants we will include random effect terms for each subject.
